C3.4. Urine metabolites of cannabis will be compared to neuroimaging and cognitive indices. From urine, we will assay 11 cannabinoids and metabolites including: THC, 11-hydroxy- Δ^9 -tetrahydrocannabinol (11OH-THC), 11-nor- Δ^9 -tetrahydrocannabinol-9-carboxylic acid (THC-COOH), 11-nor- Δ^9 -tetrahydrocannabinol-9-carboxylic acid glucuronide (THC-C-gluc), cannabinol (CBN), cannabidiol (CBD), cannabigerol (CBG), cannabidivarin (CBDV), Δ^9 -tetrahydrocannabivarin (THCV), and 11-nor-9-carboxy- Δ^9 -tetrahydrocannabivarin (THCV-COOH). *This study will be the first to compare urine cannabinoids and metabolites to neuropsychological performance and imaging measures of neuroinflammation (DBSI) in virally controlled PLWH and HIV- controls.* This is important because many studies only assess frequency of cannabis use, and it is now understood that potency, not just frequency, is an important indicator of exposure.⁸⁸

C3.5 Data-driven techniques will be applied to identify novel interactions. Prior studies of cannabis use and HIV have relied on traditional statistical methods that are generally insensitive to nonlinear models and high-order interactions believed to underlie complex clinical phenotypes. Our team has significant expertise in applying data driven techniques to discover novel mechanisms of changes in brain integrity within PLWH.^{89, 90} Biomarkers of peripheral and brain inflammation, detailed brain volumetrics, cognitive scores, demographics, and other relevant clinical data will be evaluated using data driven machine learning algorithms. *This study will be the first to use machine learning based feature selection methods to identify latent relationships and conditional dependencies seen with regular cannabis use and HIV status.* These methods are applicable for high dimensional data with binary or continuous outcomes, do not depend on heuristics, are noise-tolerant, and are sensitive to feature interactions and non-linear relationships, making them the optimal choice for the identification of novel biomarkers. Moreover, the methods proposed in this application will allow us to evaluate brain integrity without being biased by *a priori* regions of interest.

D Study Design

D1 Overview or Design Summary

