A total of 160 PLWH (80 regular cannabis users and 80 non-users) and 160 demographically similar healthy HIV- controls (80 regular cannabis users and 80 non-users) may undergo multimodal neuroimaging, immunophenotyping (including blood and cerebrospinal fluid), and neuropsychological testing to address the specific aims. PLWH may be recruited from WUSTL Infectious Disease (ID) Clinic, the AIDS Clinical Trial Unit (ACTU), Volunteers for Health, The Spot, other area providers and by hanging flyers at various places in the community. HIV- controls may be recruited from similar demographic communities as the PLWH, as well as Volunteers for Health and the surrounding community and social organizations.

D2 Subject Selection and Withdrawal

D2.1 Inclusion Criteria

(1) Participants must be 18–70 years old.

- (2) PLWH must have documented HIV infection for approximately 1 year, be on a cART regimen for approximately ≥ 3 months, and be virally well-controlled (< 200 copies/mL).
- (3) HIV- controls must have confirmed HIV- serostatus.
- (4) Participants must complete at least 9 years of education.
- (5) Participants must be able to provide informed consent.
- (6) Female participants must have a negative pregnancy test or written documentation of tubal ligation, hysterectomy, post-menopausal status, etc. and cannot be breastfeeding.
- (7) Participants should have no contraindications to an MRI scan.
- (8) Participants should be willing to have cannabis use history confirmed via clinical interview and urine analysis.
- (9) All inclusion criteria at PI discretion.

D2.2 Exclusion Criteria

- (1) History of neurological disorder (e.g., stroke, epilepsy, head injury with loss of consciousness for > 5 minutes, developmental learning disability, etc.).
- (2) Uncontrolled major affective disorder; any history of schizophrenia. Major depression or Bipolar disorder controlled with no hospitalizations and suicidal ideation in the past year is allowed.
- (3) Current substance use disorder (SUD) other than cannabis use disorder (CUD) and mild Alcohol Use Disorder as defined by DSM-5 criteria. A past SUD approximately > 1 year before the time of study enrolment may be allowed.
- (4) currently prescribed anti-coagulants (only exclusionary if participant will engage in optional LP).
- (5) an allergy to lidocaine or similar anesthetic (only exclusionary if participant will engage in optional LP).

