Serious adverse events may be reported to the IRB within the timeline outlined in their policies and procedures. The stopping criteria and guidelines to be used for this protocol may include the following: 1) The study may be stopped if there is clear evidence of harm or harmful side effects of the procedures used in this protocol; 2) In the event that a serious adverse event (SAE) occurs that increases the risks to participants, the study may be stopped and an investigation be conducted and a findings report generated by the PI; 3) Should there be an SAE or adverse event (AE) that occurs at a frequency greater than 5%, it will be added to the consent document, if not already addressed, and enrollment may be halted while a determination is made regarding the potential risks to participants. The risks of the study are low, however, the PI and study physicians as well as the WUSTL IRB will review safety material and the protocol at least annually.

F Statistical Plan

Considerations for data science methods: Continuous variables will be transformed as needed prior to analyses to improve normality and linearity of the relationship to the designated outcome variable. Raw NP tests that measure time on a task will use an inverse transformation $f(t) = 1/t$, measuring the speed of task completion; for other tests an empirical normal quantile transformation and normative corrections for demographics will be considered, which will lead to scale scores and z-scores. NP global and sub-domain values are likely to be normally distributed, which will allow for multivariable linear regression. The distributions of depression, apathy, and HRQoL scores are likely to be right-skewed and over-dispersed; therefore, negative binomial regression may be considered for analyses. All statistical tests will be two-sided, with significance declared at the $p < 0.05$ level (unless otherwise stated). In addition to hypothesis testing, 95% confidence intervals (95%CI) will be determined for effect sizes of interest. Sex will be investigated as a potential predictor of interest for each hypothesis and analysis. In exploratory analyses, correction for multiple comparisons will preserve the false discovery rate (FDR) at the 0.05 level.

Demographics: Demographic, medical, psychosocial, and lab characteristics of participants will be summarized using N (%) for categorical variables, and mean, standard deviation, and range for numeric variables.

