Cannabis: The effect of regular cannabis use will be examined primarily using the grouping of individuals into cannabis users and non-users. Additional exploratory analyses will quantify exposure (KMSK and urine metabolites) and will examine the relationship between outcomes of interest and cannabis metabolites among cannabis users. Both linear and non-linear relationships, including quadratic and smooth effects via generalized additive models, will be evaluated.

Composite peripheral inflammatory response: The primary inflammatory response will be a composite, continuous variable, summarizing the level of a compartment at the individual level. The composite variable will be the first principal component (PC1) of the set of peripheral inflammatory markers (CD4/CD8 ratio, sCD14, sCD163, and monocyte subpopulations: CD14-CD16+, CD14+CD16+, CD14+CD16-) obtained via principal component analysis (PCA). Individual biomarkers will be log-transformed and standardized prior to the transformation. This amounts to standardizing each log-transformed marker to a standard deviation of 1 and creating a single composite marker, which accounts for multivariate correlations.

Composite brain inflammatory response: A composite brain inflammatory response will be created using the first principal component of a PCA transformation of CSF inflammatory markers (MCP-1 and neopterin) and cellularity derived from DBSI.

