Aim 1: *Hypothesis 1a.* The effect of regular cannabis use on peripheral and brain inflammatory markers (primary response: composite markers; secondary: individual inflammatory markers) will be analyzed using linear models (analysis of covariance), including as predictors cannabis status, HIV, and their interaction. If an interaction effect between cannabis and HIV status is not significant, additive effects will be evaluated. Demographic factors such as Wide Range Achievement Test (WRAT)-4, sex, and age will be examined as explanatory variables and incorporated into the final models if significant at $p < 0.20$ on backward model selection. Secondary marker analyses will control for multiple tests by keeping the overall FDR at level $\alpha = 0.05$. The effect of cannabis on peripheral and brain inflammatory markers among PLWH and HIV- controls will be reported based on these models using a 95%CI. In the absence of a HIV-by-cannabis interaction, the additive effects of cannabis and HIV are of primary interest. If an interaction is present, then the primary comparison will be between CB+ and CB- groups among PLWH (at $\alpha = 0.05$). Secondary analyses will compare the PLWH, CB+ to the other two groups (at familywise error rate $\alpha = 0.05$).

Hypothesis 1b. The relationship between cannabis exposure (KMSK and urine analysis of cannabis metabolites) and peripheral and brain immune activity markers (primary response: composite markers; secondary: individual markers, possibly log-transformed, as noted above) will be analyzed among regular cannabis users using linear models. Demographic factors such as the WRAT-4, sex, and age will be examined as explanatory variables and incorporated into the final models if significant at $p < 0.20$ on backward model selection. In addition to linear effects, non-linear cannabis effects will also be considered, including quadratic effects and smooth effects fitted via generalized additive models. Possible interactive effects between cannabis exposure levels and HIV will also be examined.

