Hypothesis 1b. We have $\geq 80\%$ power to detect an association between cannabis exposure and peripheral immune activity markers explaining $R^2 = 0.047$ or more of the variance in the response, corresponding to a small Pearson correlation coefficient of $r = 0.219$ or higher. This effect size is achievable. In our preliminary data, we observed higher correlation levels (Figure 4). For brain inflammatory activity

markers the corresponding values are $R^2=0.069$, $r=0.262$. The power calculations used statistical software (G*Power).

Hypothesis 1c: Sample size determination for classifier development aims will seek to improve predictor accuracy and significance.⁹⁸ Sample size determinations were conducted using proposed published methods. Training and testing errors of cross validated progressively sampled models will be assumed to follow power laws and will be evaluated based on asymptotic error value convergence to identify appropriate sample sizes.^{99, 100} Results will be optimized based on nonlinear weighted least squares fitting.¹⁰¹ Cross validated model performance will be compared using empirical and uniform priors to determine the effect of balanced classes.¹⁰² Cross validation of data with randomly permuted labels will be used to identify the significance of model results.¹⁰³

Aim 2:

Hypothesis 2a: The effect of cannabis and HIV on cognition will be quantified through linear models, similar to those discussed under Hypothesis 1a, adjusting for confounding factors. The main NP outcomes of interest are raw scores from the working memory/executive function domain scores. Secondary outcomes are cognitive domain-specific scores and global deficit score, with FDR control, as discussed above. We expect to find additive but not interactive effects of HIV and cannabis use on primary NP outcomes. Separate analyses will examine the effect of cannabis on NP outcomes, controlling for peripheral immune indices.

Analyses of brain volumetrics will focus on the hippocampus as the primary outcome. Secondary outcomes will include the caudate, amygdala, putamen, and pre-frontal regions (with FDR corrections). These volumetric analyses will follow a similar pattern to that described for NP outcomes.

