a Pearson correlation coefficient of 0.219. For comparison, in our preliminary analyses we found $r=0.23$ (Figure 3B).

Hypothesis 2c: Sample size determination for classifier development aims will seek to improve predictor accuracy and significance.⁹⁸ Sample size determinants will be conducted using proposed published methods. Training and testing errors of cross validated progressively sampled models will be assumed to follow power laws and will be evaluated based on asymptotic error value convergence to identify appropriate sample sizes.^{99, 100} Results will be optimized based on nonlinear weighted least squares fitting.¹⁰¹ Cross validated model performance will be compared using empirical and uniform priors to determine the effect of balanced classes.¹⁰² Cross validation of data with randomly permuted labels will be used to identify the significance of model results.¹⁰³

G Data Handling and Record Keeping

1. Confidentiality and Security

All data will be safeguarded in accordance with HIPAA and the principles and practices of strict confidentiality. Studies are done for research purposes only. The risks of breaching confidentiality will be rigorously limited by the use of locked and restricted access to data. No identifiers will be included in any reports generated by this study. All key personnel involved in the design or conduct of research that involves contact with human subjects will receive the required education on the protection of human research subjects prior to beginning work on this project. All electronic data transferred to Drs. [name] [name], or [name] will be de-identified and sent via encrypted email, encrypted hard drive by courier, or by providing them access to a secure database (i.e. RedCap, CNDA, WUSTL Box, etc.). All biological data sent to Temple University will be done via courier.

2. Training

All study staff must complete CITI and HIPAA training and be listed as engaged with the IRB before they will be able to perform any study procedures. Study staff must also review protocol and sign a delegation log expressing understanding and commitment to adhere to it.

3. Case Report Forms and Source Documents

Copies of participants' medical records containing data to be used in the study (i.e. lab values, diagnoses, lists of medication, etc.) should be placed in the file whenever possible. Should these source documents not be available, subject report is acceptable.

4. Records Retention

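### The 80% power stated for Hypotheses 1b and 2b holds for one unadjusted test of one exposure, but the plan names at least two exposures and labels these analyses exploratory under FDR control

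*Combined protocol and SAP*

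**What the plan says.** All of this is in the combined protocol and SAP.

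- **Power claims.** Section F, Power Analysis for Aim 1, Hypothesis 1b claims at least 80% "power to detect an association between cannabis exposure and peripheral immune activity markers" at R² = 0.047 (r = 0.219), and gives R² = 0.069 (r = 0.262) for brain markers. Power Analysis for Aim 2, Hypothesis 2b gives R² = 0.047 (r = 0.219) only, then adds "For comparison, in our preliminary analyses we found" r = 0.23. None of these statements mentions multiplicity.
- **Population.** The 1b relationship "will be analyzed among regular cannabis users using linear models". Section D1 plans "A total of 160 PLWH (80 regular cannabis users and 80 non-users") and "HIV- controls (80 regular cannabis users and 80 non-users"), so there are 160 users.
- **Exposures.** The 1b analysis paragraph uses the KMSK and the urine metabolites, whereas the hypothesis in section C1 refers to THC and CBD metabolites. The 2b analysis paragraph refers to THC and CBD concentrations. Section C3.4 says of the urine that "we will assay 11 cannabinoids and metabolites". No primary exposure is named. Quadratic and smooth terms and HIV interactions are also to be examined.
- **Status and error control.** Section F, Cannabis: "Additional exploratory analyses will quantify exposure (KMSK and urine metabolites"), with outcomes then related to metabolites among users. Section F, opening paragraph: "In exploratory analyses, correction for multiple comparisons will preserve the false discovery rate (FDR) at the 0.05 level". Yet 1b is listed under the primary aim, has a declared primary response (the composite markers) and carries a power claim. The 1b and 2b analysis paragraphs state no FDR rule of their own.

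**The concern.** The power statement and the error rule describe different analyses. One detectable correlation per outcome class implies one exposure and one test at 0.05. The analysis text has at least two exposures, and the general rules put exposure analyses under FDR. If the FDR rule applies, 80% is too high at the stated correlations. If it does not, the chance of at least one false positive per response exceeds 5%. A reader could then not tell a prespecified THC or CBD result from the best of several.

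The plan does account for multiplicity in a power figure elsewhere: the secondary group comparisons under Hypothesis 1a are quoted after Holm-Bonferroni correction. Its absence from 1b and 2b is therefore an inconsistency within the plan.

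**Working it through.** **Inputs.** Users: 80 + 80 = 160 (section D1). Brain markers: the 70% lumbar puncture completion in the Hypothesis 1a power paragraph gives 0.70 × 160 = 112; its use for 1b is inferred, and the match below supports it. Alpha is 0.05 two-sided (section F, opening paragraph).

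**Formula (Fisher z).** Power ≈ Φ(atanh(r)·√(n − 3) − z₁₋α/₂). Detectable r at 80% power = tanh((z₁₋α/₂ + 0.8416)/√(n − 3)).

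**Step 1: the plan's own figures.**
- n = 160, r = 0.219: 2.789 − 1.960 = 0.829, power 79.7%. The noncentral F model gives 80.6%.
- n = 112, r = 0.262: 2.801 − 1.960 = 0.841, power 80.0%. Noncentral F gives 81.3%.

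Both reproduce as one two-sided test at 0.05. A one-sided test would give about 87-88% and does not fit.

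**Step 2: two exposures (THC and CBD).** The first step of Holm, or of Benjamini-Hochberg with one true association, is close to α = 0.05/2 = 0.025 (z = 2.241).
- n = 160: 2.789 − 2.241 = 0.548, power 70.8% (noncentral F 71.7%). Detectable r is 0.241 (noncentral F 0.239).
- n = 112: 2.801 − 2.241 = 0.559, power 71.2% (noncentral F 72.5%). Detectable r is 0.287 (noncentral F 0.283).

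**Step 3: twelve exposures, 1b only.** KMSK + 11 analytes = 12. With one true association the threshold is about 0.05/12 = 0.00417 (z = 2.865).
- n = 160: 2.789 − 2.865 = −0.076, power 47.0% (noncentral F 47.5%). Detectable r is about 0.285-0.288.
- n = 112: 2.801 − 2.865 = −0.065, power 47.4% (noncentral F 48.2%). Detectable r is about 0.336-0.341.

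**Step 4: Benjamini-Hochberg simulation.** FDR is less severe than Bonferroni when several exposures are truly associated. Per-exposure power at the stated r, 8,000 data sets per scenario:

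| Exposures tested | Truly associated | n = 160, r = 0.219 | n = 112, r = 0.262 |
|---|---|---|---|
| 2 | 1 | about 72% | about 72% |
| 2 | 2 (mutual correlation 0.3) | about 77% | about 78% |
| 12 | 1 | about 48% | about 48% |
| 12 | 3 | about 58% | about 58% |
| 12 | 6 (mutual correlation 0 or 0.5) | 65-66% | 66-67% |
| 12 | 12 (mutual correlation 0.6) | about 73% | about 75% |

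The numbers truly associated and their mutual correlations are assumptions; the documents give neither.

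**Step 5: the 2b preliminary value.** At r = 0.23 and n = 160, noncentral F gives 84% power at α = 0.05 and 77% at α = 0.025.

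**Step 6: if nothing is corrected.** The chance of at least one false positive per response is 1 − 0.95² = 9.75% for two independent tests and 1 − 0.95¹² = 46% for twelve. It is lower if the tests are positively correlated.

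**The case against.** The best defence is that nothing was miscalculated: the figures are right for the test they describe. That stands. The gap lies between the power statement and the multiplicity rule.

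A reader might infer that 1b and 2b have only even odds of success. The documents do not support that, for four reasons.

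- They never say that each analyte is tested separately. Section C3.4 describes an assay panel (its list names ten of the eleven), so twelve tests is an inferred upper count on the exposure side.
- That count suits only 1b. The 2b analysis names THC and CBD alone, and r = 0.262 is not a 2b figure.
- About 48% is the least favourable FDR case, with exactly one of twelve exposures truly associated. The panel includes THC together with several of its own metabolites, so a real THC association would probably appear in more than one analyte.
- The 1b power paragraph reports preliminary correlations above the stated values. The figure is not shown, so the practical shortfall for 1b cannot be judged.

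It can also be said that 1b is not exploratory at all, since it sits under the primary aim with a primary response. That is a fair reading, but it conflicts with the Cannabis paragraph of section F. It also leaves two or more exposures with no stated error control. Finally, naming one primary exposure would make the present figures correct for that test. That is so, but the plan does not name one.

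**Conclusion.** The point holds in a limited form. The stated 80% applies to one unadjusted two-sided 0.05 test of one exposure: n = 160 for 1b peripheral markers and for 2b, and n = 112 for 1b brain markers. Under the plan's own FDR rule, with the two exposures the hypotheses name, power at those correlations is about 71-72% if one is truly associated and 77-78% if both are, a loss of roughly 2 to 9 points. The wider range for 1b, about 48% to about 73%, applies only if the KMSK and all 11 analytes are tested separately. The 2b preliminary r = 0.23 keeps about 77% power at α = 0.025, so it no longer clears 80% once two exposures share the error rate.

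This rests on reading the exploratory label and the FDR rule together as covering 1b and 2b, and on 70% lumbar puncture completion for brain markers. The conflict between that label and the standing of 1b as a powered hypothesis under the primary aim needs to be reconciled in either case.

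**What to change.** State in section F whether Hypotheses 1b and 2b are confirmatory or exploratory. Then take one of two options, which are equally acceptable:

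- **(a)** Name one THC-derived and one CBD urine measure, linear term, as the primary exposures, with Holm across the two. Restate detectable r as about 0.24 (n = 160) and about 0.28 (n = 112; 0.283 by noncentral F, 0.287 by Fisher z).
- **(b)** Name a single primary exposure per hypothesis, tested at 0.05, and keep r = 0.219 and r = 0.262 for that test only.

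Under either option, keep the remaining exposure analyses (the KMSK, other analytes, non-linear forms and HIV interactions) as exploratory. Define the FDR family they belong to and attach no 80% power claim to them.

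The cost is SAP wording and, under (a), slightly less favourable stated figures. Sample size and study procedures do not change.

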Hypothesis 1c: Data driven classification models will reveal novel mechanisms and associations between regular cannabis use and peripheral and brain immune activity indices (e.g. CD4/CD8 ratio, sCD14, sCD163, MCP-1, neopterin, and monocyte subpopulations, and cellularity) that differentiate HIV serostatus from cannabis use.

C2 Secondary Aim

Specific Aim 2. Cannabis use impairs cognitive performance and brain structure in both PLWH/CB+ and CON/CB+.

Hypothesis 2a: Cognitive performance (particularly working memory and executive function) and brain volumetrics (temporal and parietal lobes) will be worse in regular cannabis users regardless of HIV status.

Hypothesis 2b: The effects of cannabis on brain integrity will be moderated by THC and CBD concentrations.

Hypothesis 2c: Data-driven classification models will reveal novel highly dimensional mechanisms and associations between cannabis use and brain integrity that differentiate HIV serostatus from cannabis use.

C3 Innovation and Rationale for the Selection of Outcome Measures

3. Innovation

C3.1 Quantitative evaluation of both peripheral and brain markers of immune activity and inflammation will improve our understanding of the effects of regular cannabis use in PLWH. We will evaluate the effects of regular cannabis use on validated plasma and CSF markers of immune health and inflammation. This proposal will be the first to simultaneously acquire extensive phenotype data from peripheral and brain markers of immune function (e.g., CD4/CD8 ratio, peripheral monocyte subsets, plasma sCD14, and sCD163 and CSF MCP-1 and neopterin), brain structure (volumetrics), brain inflammation (cellularity), and cognition (neuropsychological performance (NP) testing) in virally controlled PLWH on cART and HIV- controls. Immune responses will be examined with regards to duration, frequency, type, and amount of cannabis used.

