Hypothesis 2b: The effect of THC and CBD concentrations among cannabis users on NP and brain volumetrics will be analyzed using linear models. Demographic factors such as the WRAT-4, sex, and age will be examined as explanatory variables and will be incorporated into the final models if significant at $p<0.20$ in backward model selection. Possible non-linear cannabis effects will be explored, including quadratic effects and smooth effects fitted via generalized additive models. A possible interaction between cannabis exposure levels and HIV will also be examined.

Hypothesis 2c: Data-driven feature selection methods⁹²⁻⁹⁵ will be performed to reveal highly dimensional mechanisms and associations between cannabis use and brain integrity (cognition and volumetrics) that differentiate HIV serostatus from regular cannabis use. The analysis will yield a subset of biomarkers that are most indicative of the effects of cannabis on brain integrity (NP and volumetrics), while excluding irrelevant and redundant biomarkers. Continuous variables will be normalized to zero mean and unit variance. Features will be scaled independently to a common interval to ensure that features with higher magnitudes are not given preference during training. All analysis will be conducted with 10-fold cross validation with 10 repeats to ensure the reliability of the results.⁹⁶ Individual models will be trained with a categorical cross entropy loss function, and evaluated based on sensitivity, specificity, and receiver operator curve (ROC) area under the curve (AUC) F1 analyses. Models will be compared using the mean misclassification rate and Bayesian information criteria.⁹⁷ All analysis will be performed in common programming languages and packages (MATLAB, Python, and R).

Power Analysis for Aim 2:

Hypothesis 2a: With the proposed sample size of $n=320$ we have $\geq 80\%$ statistical power to detect additive effects of HIV status and cannabis use on NP and volumetrics outcomes corresponding to Cohen's $d=0.314$ each. This effect size is consistent with those determined in our preliminary data (Cohen's $d=0.584$ for cannabis and $d=0.418$ for HIV in *Figure 5*).

Hypothesis 2b: We have $\geq 80\%$ power to detect an effect of cannabis exposure among cannabis users on NP or volumetric outcomes corresponding to $R^2=0.047$ proportion of variance explained, or equivalently

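### Hypothesis 2a predicts smaller parietal volumes but the plan pre-specifies no parietal test, and head-size adjustment of the volumetric outcomes is not pre-specified

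*Combined protocol and SAP*

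**What the plan says.** Section C2 (Secondary Aim), Hypothesis 2a, predicts that "brain volumetrics (temporal and parietal lobes) will be worse in regular cannabis users regardless of HIV status".

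Section F, Aim 2, Hypothesis 2a, sets the outcomes. The primary one is given as "Analyses of brain volumetrics will focus on the hippocampus as the primary outcome". Then: "Secondary outcomes will include the caudate, amygdala, putamen, and pre-frontal regions (with FDR corrections").

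On the model, the same paragraph says: "These volumetric analyses will follow a similar pattern to that described for NP outcomes". The cognitive (NP) models in turn refer back to Hypothesis 1a and add a general statement that confounders will be adjusted for. Hypothesis 1a names WRAT-4, sex and age as examples of covariates, each retained only if p<0.20 on backward selection. Hypothesis 2b applies the same set and the same rule to volumetrics. Intracranial volume, head size and normalised volume are not mentioned anywhere in the document.

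The Power Analysis for Aim 2 gives at least 80% power at n=320 for additive effects of HIV and cannabis on cognitive and volumetric outcomes, "corresponding to Cohen's $d=0.314$ each".

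**The concern.** There are two separate gaps.

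First, the hypothesis and the outcome list do not match. If a result is to confirm or refute the parietal prediction, a parietal volume has to be among the pre-specified outcomes. Without that, any parietal comparison is post hoc and has no defined place in the FDR family.

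Second, a covariate set built for cognition has been carried over to volume. WRAT-4 is a natural covariate for test scores; head size is the natural one for regional volume. If head size predicts volume, leaving it out keeps avoidable variance in the residual. The groups are also not randomised: section D3.1 says controls are matched demographically only as far as possible, and it describes no matching of cannabis users to non-users. A systematic head-size difference would therefore pass into the volume contrast. If the choice is not fixed in advance, whether and how to correct for head size can be decided after the data are seen.

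**Working it through.** **1. Hypothesis against outcome list**

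| Named in Hypothesis 2a | Pre-specified volumetric outcome |
|---|---|
| Temporal lobe | Hippocampus (primary) and amygdala (secondary), both medial temporal; no whole-lobe volume |
| Parietal lobe | None |
| Not named | Caudate, putamen, pre-frontal regions (secondary) |

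Hypothesis 2c is the only other planned use of volumetrics by region. It selects features that classify HIV and cannabis status. It does not estimate or test whether parietal volume is lower in users.

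**2. Reproducing the plan's power figure**

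Inputs: two-sided 0.05 and 80% power (section F); four cells of 80 (section D1), so each main effect compares 160 with 160.

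Detectable d = (1.960 + 0.842) × √(2/160) = 2.802 × 0.1118 = 0.313 by the normal approximation. The noncentral t gives 0.3142, with power 79.96% at d=0.314. The stated figure reproduces, as a comparison with no covariates.

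**3. Gain from a head-size term**

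Let r be the within-group correlation of head size with regional volume. The documents give no value, so 0.3 to 0.6 is assumed. Let s be the correlation of sex with head size, assumed 0.5 to 0.6, with sex acting on volume only through head size.

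- Detectable d with head size in the model: 0.314 × √(1 − r²).
- Sample-size multiplier against no covariates: 1/(1 − r²).
- Sample-size multiplier against a model that already has sex: (1 − r²s²)/(1 − r²).

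| r | Detectable d | Power at 0.314 (noncentral t) | Gain v no covariates | Gain v sex retained, s=0.5 | Gain v sex retained, s=0.6 |
|---|---|---|---|---|---|
| 0.3 | 0.300 | 83.5% | 10% | 7% | 6% |
| 0.4 | 0.288 | 86.3% | 19% | 14% | 12% |
| 0.5 | 0.272 | 89.9% | 33% | 25% | 21% |
| 0.6 | 0.251 | 93.8% | 56% | 42% | 36% |

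Worked corner values: r=0.3, s=0.6 gives (1 − 0.0324)/0.91 = 1.063; r=0.6, s=0.5 gives (1 − 0.09)/0.64 = 1.422.

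**4. Would sex be retained?**

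Under these assumptions sex correlates r × s with volume, at least 0.3 × 0.5 = 0.15. With N=320, z = atanh(0.15) × √317 = 2.69. The p<0.20 threshold is 1.28, so retention has probability Φ(1.41), about 92%, at the weakest corner. The comparison with sex retained is therefore usually the relevant one.

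**5. Bias**

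A systematic head-size difference of δ SD that sex does not explain biases the contrast by r × δ. For illustration, δ=0.2 and r=0.5 (both assumed) give 0.10 SD, about a third of 0.314. With no true effect, that would raise the false-positive rate from 5% to about 14.5%. The documents give no evidence that such a difference exists.

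**The case against.** The strongest reply is that the plan's silence is not a decision. It speaks of adjusting for confounders, gives its covariates as examples, and describes no volumetric processing: no structural sequence, no segmentation method and no definition of volume. A reader might infer that raw, unadjusted volumes will be compared. The documents do not say so; volumes might be normalised before modelling. What stands is that none of this is pre-specified.

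Sex and age are already candidate covariates, and section F says sex will be investigated in every analysis. That is why the 10-56% range alone would overstate the gain. Sex handles most of a sex-mix imbalance, but not head-size variation within sex.

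Power looks ample at the preliminary effects: 99.9% at d=0.584 and 96.1% at d=0.418, unadjusted. This is fair for effects of that size, although the figure behind them is not shown and they may not be volumetric. The precision loss matters mainly near or below 0.314. At d=0.25, power is 60.6% unadjusted and 73.0% with head size at r=0.5. Hypothesis 2b also has little room: the preliminary r=0.23 is close to the detectable 0.219.

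It is tempting to count a chance head-size imbalance as bias. It is not. A 0.2 SD gap is 0.2/0.1118 = 1.8 standard errors (p about 0.07), and the unadjusted standard error already carries that variation.

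A reader might also infer that the parietal lobe will never be examined. The secondary list is worded openly, and the data-driven models are not tied to chosen regions, so it could be. Neither route is a pre-specified test of the hypothesis.

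**Conclusion.** The mismatch is documented and needs no assumption: the parietal part of Hypothesis 2a has no pre-specified test, and the temporal part is covered only by hippocampus and amygdala.

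The head-size point is an omission from the pre-specification. Its direction is clear if head size predicts regional volume. Its size rests on assumed correlations: a gain equivalent to about 6-42% more participants if sex is already in the model, or 10-56% if nothing is. Bias is conditional on a systematic head-size difference beyond sex, which the documents neither show nor exclude.

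A reader might conclude that the power statement is wrong or that Aim 2 is underpowered. Neither follows, since d=0.314 is correct for the comparison it describes. The point concerns a secondary aim, and it merits a change because the repair is cheap.

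**What to change.** 1. Add parietal-lobe volume and total temporal-lobe volume to the FDR-controlled secondary volumetric outcomes, or amend Hypothesis 2a to name only the regions tested.
2. State how volumes are derived. Pre-specify intracranial volume as a covariate (or head-size-normalised volumes), and force it in, together with age and sex, in every volumetric model, including Hypothesis 2b. These terms should not pass through the p<0.20 selection.

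The cost is plan wording and values that should be derivable from the planned scans. The documents do not describe the imaging pipeline, so this should be confirmed. There is no new participant or visit.

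The statistical price is a slightly stricter FDR step. If pre-frontal counts as one region, the volumetric regions form their own family and a Benjamini-Hochberg procedure is used (the plan does not name one), the threshold for the smallest p-value moves from 0.05/4 = 0.0125 to 0.05/6 = 0.0083.
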